4.2 Selection of study population

4.2.1 Inclusion criteria

A patient must fulfill the following criteria in order to be included in the study:

1. Informed consent obtained from the patient's legally authorized representative(s)
2. Patients with MPS IIIA, as confirmed by both:
 - A documented deficiency in sulfamidase enzyme activity in concordance with a diagnosis of MPS IIIA*, and
 - Normal enzyme activity level of at least one other sulfatase measured in leukocytes
3. Chronological age of ≥ 12 and ≤ 72 months (i.e., 1 to 6 years) at the time of the first SOBI003 infusion and has a developmental age ≥ 12 months at screening as assessed by the VABS-II
4. Medically stable patient who is expected to be able to comply with study procedures

* as determined by the reference ranges applied by the Greenwood Genetic Center

4.2.2 Exclusion criteria

The presence of any of the following will exclude a patient from inclusion in the study:

1. At least one S298P mutation in the N-sulfoglucosamine sulfohydrolase (SGSH) gene
2. Contraindications for anesthetic procedures, surgical procedure (venous access port), MRI scans and/or lumbar punctures
3. History of poorly controlled seizures
4. Patients is currently receiving psychotropic or other medications which in the investigator's opinion, would be likely to substantially confound test results
5. Significant non-MPS IIIA-related central nervous system (CNS) impairment or behavioral disturbances, which in the investigator's opinion, would confound the scientific integrity or interpretation of study assessments
6. Prior administration of stem cell or gene therapy, or enzyme replacement therapy (ERT) for MPS IIIA
7. Concurrent or prior (within 30 days of enrolment into this study) participation in a study involving invasive procedures

4.3 Method of treatment assignment and randomization

This is a non-randomized, open-label study; no blinding of treatment assignments is required.

Upon provision of signed informed consent, patients are assigned a site-specific enrolment number in consecutive order. Upon completion of the screening assessments and confirmation of patient eligibility, patients are allocated to a dose cohort in consecutive order, with prioritization

of the younger patients. There is thus no restriction or requirement regarding the site distribution of patients per cohort, i.e., patients within one cohort can be recruited at only one site or at multiple sites.

5 Sequence of planned analysis

5.1 Safety review committee

Treatment initiations will be staggered within each cohort in order to be able to observe, interpret and treat possible adverse reactions and to ensure that such reactions can be dealt with promptly. For each cohort, SRC meetings are scheduled approximately 3 weeks after completion of the 3rd patient's 4th dose administration. Based on the safety, immunogenicity, PK and PD data, it is the responsibility of the SRC to determine:

- whether dosage of ongoing cohort(s) can continue
- if the infusion time and rate of subsequent administrations at ongoing dose level should be altered
- whether it is safe to continue to the next cohort, i.e., to expose new study patients to SOBI003 treatment
- the SOBI003 dose to be administered in the next cohort and to ongoing patients in the extension study (SOBI003-002).

Additional SRC meetings will be scheduled *ad hoc* as per principal investigator or Sobi SRC member requests. The SRC will review cumulative data from both the FIH study (SOBI003-001) and the extension study (SOBI003-002).

An SRC charter will specify the operating procedures including SRC membership, voting members, responsibilities, data review meeting details, and lines of communication with the study teams at Sobi, Syneos Health, and investigational sites.

The SRC charter will also specify in detail the data and outputs presented in the SRC summary reports, which will be provided to the SRC members for their review.

5.2 Data safety monitoring committee

In addition to the SRC, a DMC is assigned to monitor safety, PK, PD, and immunogenicity data. The primary responsibility of the DMC is to provide additional safety oversight of the study conduct in order to further protect study participants.

A DMC charter will specify the operating procedures including DMC membership, responsibilities, data review meeting details, and lines of communication with the study teams at Sobi and Syneos Health.

The DMC charter will also specify in detail the data and outputs presented in the open reports, which will be provided to the voting members of the DMC for their review.

The DMC will review cumulative data from both the FIH study (SOBI003-001) and the extension study (SOBI003-002). The first DMC review meeting will be held 6 months following first patient visit in the extension study and will occur every 6 months until completion of the extension study. If requested by Sobi or DMC, additional ad-hoc meetings may be held.

5.3 Interim analyses

No interim analysis is planned for this 24-week study.

5.4 Analyses and reporting

All final, planned, analyses identified in the CSP and in this SAP will be performed only after the last patient has completed the study. Tables, listings, and figures to be provided for SRC and DMC review are specified in separate SRC Listing and SRC Table shell documents.

Any post-hoc analyses included in the CSR, which were not identified in this SAP, will be clearly identified as such in the relevant section of the CSR.

6 Sample size determination

Given that this is a FIH study with no formal hypothesis tests, no sample size calculation has been performed. Three sequential dose levels with 3 patients in each cohort was considered sufficient to allow assessment of safety and tolerability concerns, as well as characterize a PD dose-response relationship in this rare population with a high unmet medical need.

7 Analysis sets

The following analysis sets will be used in the statistical analyses. Analyses will be performed by dose cohort; in addition, summary tables will be presented for all patients.

For PK and PD, analyses will be performed by dose level as described in Section 15 and 16.

7.1 Safety analysis set (SAF)

The SAF is the primary analysis set and will consist of all patients who received at least 1 dose of investigational medicinal product (IMP).

The SAF will be used for the safety analyses.

7.2 Full analysis set (FAS)

The FAS will consist of all patients who have a baseline and at least 1 post-baseline assessment of any secondary or exploratory assessment.

The FAS will be used for the secondary and exploratory efficacy analyses.

7.3 PK analysis set (PKAS)

The PKAS will consist of all patients where at least 1 SOBI003 dose has been administered correctly and where SOBI003 serum or CSF concentration data is available without any protocol deviation interfering with these results.

The PKAS will be used for the analysis of PK secondary endpoints relating to the 1st secondary objective.

7.4 Immunogenicity analysis set

The immunogenicity set will consist of those patients in the safety analysis set who have sufficient blood samples taken for ADA testing at baseline and at least 1 post-dose time-point.

The immunogenicity set will be used for the immunogenicity analyses.

In case any patient has missing baseline, a second immunogenicity analysis set will be formed including all patients with sufficient blood samples for ADA testing (i.e. including those with missing baseline). All immunogenicity analyses without considering baseline will be performed on that second set.

8 General issues for statistical analysis

All statistical tests will be two-sided and performed using a 5 % significance level, if not stated otherwise. Results will be presented as the estimated mean value for each treatment group, the estimated difference between groups, the associated 95 % two-sided confidence interval and P-value. P-values from statistical analyses will be presented to three decimal places with values below 0.001 displayed as <0.001 and confidence intervals will be presented to one more decimal places than the raw data.

Continuous data will be summarized using descriptive statistics: number of patients (n), mean, standard deviation (SD), standard error of the mean (SE), median, minimum and maximum values, unless otherwise indicated. Minimum and maximum values will be presented to the same number of decimal places as the raw data and mean, SD, SE of the mean and median will be presented to one more decimal place than the raw data. Summary tables over all patients will include in addition the first quartile (Q1) and the third quartile (Q3), presented to one more decimal place than the raw data.

Categorical data will be summarized using frequency counts and percentages. Percentages will be suppressed when the count is zero, however the category will still be displayed. The denominator for all percentages will be the number of patients within the treatment group for the population of interest, unless otherwise indicated. Percentages will be presented to one decimal place.

Data for the FIH SOBI003-001 study (up to Week 24) and extension study SOBI003-002 (Week 25 to 104) will be collected in a combined database. All analyses specified in this SAP refer to FIH study SOBI003-001, i.e. for data up to Week 24.

Data obtained up to Week 24 will be summarized in tables by dose cohort, visit, and time point, if applicable. All data obtained up to Week 24 will be listed in individual patient data listings, which will be sorted by dose cohort and patient ID.

If not specified otherwise for the purpose of tabulations, the unscheduled post-baseline values will generally be excluded.

Statistical analyses will be performed using SAS software Version 9.4 or later (SAS Institute Inc, Cary, North Carolina, United States).

8.1 Handling of missing data and outliers

For all questionnaires and scales, (see Section 13.1 for more details) items that are not answered by the patient will remain as missing. If applicable, specific rules for the calculation of each score are also defined in Section 13.1.

Complete missing or partial dates will be presented in the listings as reported on the electronic case report forms (eCRFs).

If an AE has a completely missing onset date, then the AE will be considered a TEAE, unless the (partial) stop date indicates differently. A medication with a completely missing start date is considered a prior medication. A medication with a completely missing stop date is considered a concomitant medication.

If an AE or a medication has a partial missing start or stop date, the rules presented in Table 4 will be used to impute the date. The imputed date will be used to determine whether it is a TEAE for AE, or a prior or concomitant medication.

Table 4 Partial date derivation

Partial Missing Start or Stop Date	Derived Start Date	Derived Stop Date
Missing month and day, and the year is present	January 1 st of that year or first dose date if the year is the same as the year of first dose date	December 31 st of that year
Missing day, but year and month are present	First day of that month or first dose date if the year and month are the same as the year and month of first dose date	Last day of that month
Missing month, but year and day are present	Missing month derived as January or same as first dose month if the year is the same as the year of first dose	Missing month derived as December

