The results of the above assessments will constitute the patient's baseline.

The patient should not have evidence of ongoing infection, as judged by the investigator. In such case, the 1st infusion should be postponed until the infection has resolved. Antibiotic treatment should also be completed, when applicable, prior to start of SOBI003 treatment.

Within 30 to 60 minutes prior to start of the SOBI003 infusion, a single dose of an oral non-sedative antihistamine is administered. A pulse-oximeter is applied and SOBI003 infusion is initiated. Refer to Section 7.4.6 for infusion details. Day 1 of Week 1 constitutes the day of the first SOBI003 infusion.

Adverse events and concomitant medications are captured continuously from the start of the first infusion until study completion.

At hourly intervals during the infusion, (i.e., at approximately 1, 2 and 3 hours after start of infusion) vital signs, general appearance and skin are assessed.

Upon completion of the 4-hour infusion, and as soon as practically possible, a PK blood sample is obtained. Within an hour of completion of the infusion, vital signs, general appearance and skin are assessed. In addition, a 12-lead ECG is obtained and the continuous pulse oximetry is discontinued.

Vital signs (including oxygen saturation), general appearance and skin are assessed on Day 1 (within 6 to 7 hours after start of infusion, and also within 8 to 12 hours after start of infusion) and on Days 2, 3 and 5.

Blood and urine is collected for safety laboratory analyses on Day 3. Blood is collected for PK analyses at Days 1, 2, 3, 5, and 6 at time points specified in Section 7.5.6.1.

Well in advance of discharge at Week 3, the parents/caregivers will be trained on signs and symptoms of acute and delayed hypersensitivity reactions (both verbally and in writing), and informed on the importance to seek immediate medical attention if hypersensitivity reactions occurs. Acute hypersensitivity reactions include rash, itching, sweating, swelling of lips/tongue/face, vomiting, noisy breathing, dizziness, fainting, and delayed reactions includes dermatological events/skin reactions such as contact dermatitis, maculopapular rash/eruptions,

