10.2.1 MPS IIIA diagnosis

Information on diagnosis date and prior MPS IIIA diagnostic procedures will be captured in the eCRF including assessment date, diagnostic method used and test result. Summary statistics will be presented for diagnostic status and time since diagnosis (defined in [9.4.9](#)). All data will be listed.

11 Prior and concomitant medication

Prior medications will be defined as any medications taken prior to the date of 1st study treatment. Concomitant medications will be defined as medications ongoing or with a start date on or after the date of the 1st study treatment or a stop date on or after the date of the 1st study treatment.

All prior and concomitant medication will be coded using the latest version of world health organization drug dictionary (WHO-DD). Data will be listed and summary tables will be presented by anatomical therapeutic chemical classification [ATC] level 4, and WHO-DD preferred term using the SAF.

Prior to each infusion of SOBI003, a single dose of non-sedative antihistamine will be administered. Antihistamine administration including date and time, medication name, dose, unit and route will be listed and summarized per visit.

For patients continuing in the extension study (SOBI003-002), any medications with onset after the 1st dose of study drug in the extension study will not be presented in the tables and listings of the FIH study (SOBI003-001) but in the tables and listings of the extension study.

12 Treatment compliance

There will be no measurement of, or analysis of, treatment compliance, nor does it affect population assignment (patients must be exposed to study drug to qualify for the analysis sets).

13 Efficacy analyses

Efficacy data will be summarized descriptively by dose cohort, visit, and time point using the FAS.

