14.2 Adverse events

The primary endpoints are TEAEs and SAEs.

For the FIH study (SOBI003-001), all AEs (defined in CSP Section 7.5.5.1.1) occurring after the patient has received the 1st dose of investigational medicinal product and up to Day 7 of Week 24 (End of Study) will be recorded on the AE eCRF page.

For the FIH study, SAEs will be reported from the time the ICF is signed until 28 days past the last dose of study drug.

For patients continuing in the extension study (SOBI003-002), the period for recording AEs, including SAEs, on the eCRF begins Day 1 upon signing of the study ICF on Week 25 and ends Day 8 of Week 104 (End of Study) (see CSP Section 7.5.4.1.2). This includes all events observed/diagnosed or reported since the last visit of the FIH study (Week 24 / End of study).

For patients continuing in the extension study (SOBI003-002), any AEs and SAEs with onset after the 1st dose of study drug in the extension study will not be presented in the tables and listings of the FIH study but in the tables and listings of the extension study.

A TEAE is any AE with onset or worsening reported from the time that the 1st dose of study drug is administered until completion of or early termination of the study. In addition to TEAEs, SAEs with an onset date equal to or greater than the informed consent date of the FIH study and earlier than the start date of 1st dose of study drug (non-treatment emergent) will be collected and analyzed.

AEs with missing onset dates will be considered treatment-emergent, unless the stop date indicates otherwise. In the event that only a partial start date (month/year) is available, and

month/year occurs before that of 1st dose of study drug, the AE will be considered as non-treatment-emergent. If month/year occurs on, or after that of 1st dose of study drug, the AE will be considered as treatment emergent. If an AE has a partial missing start or stop date, the rules in Section 8.1 will be used to impute the date.

All AEs will be coded using MedDRA to give a PT and a SOC term for each event. The latest version of MedDRA will be used.

The severity grading is based on the national cancer institute common terminology criteria (NCI CTCAE) (version 4.03), see CSP Section 7.5.5.13.

If the causality assessment (related, not related) of a TEAE is missing, the event will be considered as drug-related following the worst case principle. Non-treatment emergent SAEs with missing causality assessment are considered not related.

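### The SAP's partial-date rule moves a start date to first dose without checking the stop date, so a record known to have ended before treatment can be tabulated as concomitant or treatment-emergent

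*SAP*

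**What the plan says.** SAP Section 8.1, Table 4 has three rows for partial start dates:

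- **Row 1, month and day missing:** "January 1 st of that year or first dose date if the year is the same as the year of first dose date".
- **Row 2, day missing:** the first of the month, or the "first dose date if the year and month are the same as the year and month of first dose date".
- **Row 3, month missing, day known:** "Missing month derived as January or same as first dose month if the year is the same as the year of first dose".

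The same table derives a partial stop date as the latest date it could be. The text above the table makes the result decisive: "The imputed date will be used to determine whether it is a TEAE for AE, or a prior or concomitant medication".

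SAP Section 11 says "Concomitant medications will be defined as medications ongoing or with a start date on or after the date of the 1st study treatment", and adds a stop date on or after first treatment as another route into that category. A start imputed to the first-dose date is therefore enough.

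For adverse events with only a month and year of onset, SAP Section 14.2 states: "If month/year occurs on, or after that of 1st dose of study drug, the AE will be considered as treatment emergent". It also refers back to the Section 8.1 rules.

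A stop-date exception does exist, but Section 8.1 gives it only to AEs whose onset is completely missing. Section 14.2 attaches it to the sentence on missing onset dates, not to the partial-date sentences that follow.

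**The concern.** Moving an ambiguous onset to first dose is a normal worst-case convention. It stops being one when a recorded stop date already shows that the event or medicine ended before treatment. Nothing is ambiguous then, yet the rule gives the record a start later than its own end and classifies it by that start.

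The SAP is also uneven. An AE with no onset information is protected by its stop date, while one with a known onset month is not. A medicine with no start date at all counts as prior, while one known to have started in the first-dose year is given the first-dose date. Better information can produce a worse classification.

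The situation can arise. Screening may take place up to 12 weeks before the first infusion, medication is recorded from screening, and SAEs are collected from consent. The port insertion, lumbar puncture, skin biopsy and anesthesia at Baseline all come before dosing. The AE part is confined to serious events, because non-serious AEs are recorded only from the first infusion.

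At stake are the concomitant-medication table and the split between serious TEAEs and non-treatment-emergent SAEs. Missing causality also changes meaning across that split: under SAP Section 14.2 it counts as drug-related for a TEAE and as not related for a non-treatment-emergent SAE.

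**Working it through.** The plan gives no figure to reproduce, so the check applies its rules literally to test dates.

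**Inputs.** Derived start and stop dates come from SAP Table 4, the concomitant definition from SAP Section 11, TEAE status from SAP Sections 8.1 and 14.2, and cohort sizes (3 and 3) from SAP Section 4.1. *Assumption:* first dose on 20 June 2019, for illustration, because the documents give no patient dates.

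**Classification rule as written.** A medicine is concomitant if its derived start or its stop is on or after first dose. An AE is treatment-emergent if its derived onset is on or after first dose.

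**Step 1: worked cases.**

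| Table 4 row | Reported start | Reported stop | Derived start | Class under the SAP | Correct? |
|---|---|---|---|---|---|
| 2 | June 2019 | 10 June 2019 | 20 June 2019 | concomitant / TEAE | No: start 10 days after stop |
| 1 | 2019 | 14 Feb 2019 | 20 June 2019 | concomitant / TEAE | No: start 126 days after stop (14+31+30+31+20) |
| 1 | 2019 | May 2019 (derived 31 May) | 20 June 2019 | concomitant / TEAE | No: start 20 days after derived stop |
| 3 | day 25, 2019 | 2 Mar 2019 | 25 June 2019 | concomitant / TEAE | No |
| 3 | day 5, 2019 | 2 Mar 2019 | 5 June 2019 | prior / non-treatment-emergent | Class correct, though start is after stop |
| 2 | May 2019 | 20 May 2019 | 1 May 2019 | prior / non-treatment-emergent | Yes |

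Row 3 moves the month and keeps the day. It misclassifies only when the reported day is on or after the first-dose day.

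**Step 2: is the row 2 error occasional or certain?** If first dose is on day D of the month, the number of true start/stop pairs lying wholly before it in that month is (D−1)×D/2.

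- D = 5: 4×5/2 = 10 pairs, 10 misclassified
- D = 15: 14×15/2 = 105 pairs, 105 misclassified
- D = 20: 19×20/2 = 190 pairs, 190 misclassified
- D = 28: 27×28/2 = 378 pairs, 378 misclassified

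This follows directly from the rule, since the derived start is D whatever the true start or stop. Row 1 behaves the same way across the whole year. These counts show that the error is certain for such records; they do not show how common such records are.

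**Step 3: largest effect of one record.** If the patient has no other record in the same table cell, the incidence changes by 1/3 = 33 percentage points in a cohort, or 1/6 = 17 points over all 6 patients. If the patient already counts in that cell, the incidence does not change.

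**Step 4: test of the stop-date check.** The rule tested keeps the start unmoved when the reported or derived stop precedes first dose, and uses the earliest possible date instead. June 2019 with stop 10 June then gives 1 June. Year 2019 with stop 14 February gives 1 January. Day 25 of 2019 with stop 2 March gives 25 January. All become prior or non-treatment-emergent. Start June 2019 with stop June 2019 (derived 30 June), or with stop 1 July, is unchanged and stays concomitant or treatment-emergent.

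**The case against.** The strongest case against is that little depends on this. Six patients are analyzed, safety and efficacy summaries are descriptive, there are no efficacy subgroups, and the HS modelling has been dropped. SAEs must be reported within 24 hours with follow-up, so a partial onset date with a known stop should be rare, and the investigator is required to assess causality. SAP Section 8.1 keeps reported dates in the listings, so a reader could trace an odd record. A programmer might also extend the stop-date exception in Section 14.2 to partial dates. Most of this stands as a limit on size. The last part does not: the partial-date sentences carry no condition, and Section 8.1 ties the exception to completely missing onset.

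Several stronger readings are tempting but not supported:

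- **The drug disappears from the prior table.** SAP Section 11 defines prior as taken before first treatment, and the two categories are not exclusive. A medicine with a pre-dose stop may still be counted as prior. What is certain is that it enters the concomitant table.
- **A finished antibiotic course would look like a protocol breach.** Protocol Section 7.5.1.4 says "Antibiotic treatment should also be completed, when applicable, prior to start of SOBI003 treatment", but infections at later infusions and other necessary therapy are foreseen, so an antibiotic in the concomitant table signals nothing by itself. Deviations are reported separately.
- **Ongoing melatonin or genistein would look newly started.** An ongoing drug is concomitant under any rule, and the planned tables do not separate stable from changed regimens. The documents do not say that these drugs affect HS.
- **The primary endpoint is inflated.** That endpoint is TEAEs and SAEs together, so a pre-dose SAE already belongs to its SAE component. The error moves it into the TEAE tables; it does not create an additional SAE.

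**Conclusion.** The defect is real and narrow. For a record whose partial start matches the first-dose month or year and whose reported or derived stop precedes first dose, rows 1 and 2 of Table 4 always give the wrong class. Row 3 does so only when the reported day is on or after the first-dose day, so a claim that every such record is misclassified goes too far. This is a stated rule that gives a wrong answer, not a detail left open.

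The practical effect is probably small: the documents do not show how many records qualify, and medicines are likelier than SAEs. The 33- and 17-point figures are upper limits for one record. The worked dates are assumed, but the result for rows 1 and 2 does not depend on them.

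A reader might also infer that every partial medication start should go to the earliest possible date. That does not follow. A medicine actually started on 25 June after a first dose on 20 June, recorded only as June, would be placed at 1 June and tabulated as prior, which hides an on-treatment start. Only the stop-date check follows from the defect.

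**What to change.** Add to SAP Table 4: *If the reported or derived stop date is before the first dose date, the start date is not moved to the first dose date or month; the earliest possible date, not later than the stop date, is used, and the record is prior (medication) or non-treatment-emergent (AE).*

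Make the partial-date sentence in SAP Section 14.2 subject to the same condition. Keep the existing rule for all other partial dates, including those of medications. Because derived stop dates already take the latest possible date, the check applies only when the record certainly ended before treatment, and every ambiguous record keeps the worst-case handling.

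The cost is one added sentence, one aligned sentence and one programming condition, with no new data collection.
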